### 8.2.6. Other Pulmonary Information

As indicated in the SoA (Section 1.3), at each timepoint for which PFTs are performed, the following information should be collected and noted in the eCRF:

- Number and severity of pulmonary exacerbations (characterized by dyspnea and/or cough and sputum that worsen over ≤14 days) since the last visit;
  - Mild exacerbation: Worsening of symptoms that can be self-managed and resolved without systemic corticosteroids or antibiotics.
  - Moderate exacerbation: Increase in symptoms that requires treatment with antibiotics and/or corticosteroids
  - Severe exacerbation: Need for hospitalization
- Smoking status, including number of cigarettes (or equivalent) per day
- Use of AAT replacement therapy (yes/no) since the last visit
- Modified Medical Research Council dyspnea score (adapted from Fletcher et al., 1959)
  - Grade 0: The patient only gets breathless with strenuous exercise
  - Grade 1: The patient gets short of breath when hurrying on level ground or walking up a slight hill
  - Grade 2: On level ground, the patient walks slower than people of the same age because of breathlessness, or have to stop for breath when walking at their own pace
  - Grade 3: The patient stops for breath after walking about 100 yards or after a few minutes on level ground
  - Grade 4: The patient is too breathless to leave the house or is breathlessness when dressing
- Resting peripheral oxygen saturation

### 8.2.7. Clinical Safety Laboratory Assessments

See Section 10.2 for the list of clinical laboratory tests to be performed and the SoA (Section 1.3) for the timing and frequency. Participants should be fasting for a minimum of 8 hours prior to the collection of blood samples as indicated in the SoA.

The Investigator must review the laboratory report, document this review, and record any clinically relevant changes occurring during the study in the AE section of the eCRF. The laboratory reports must be filed with the source documents.

All laboratory tests with values considered clinically significantly abnormal during participation in the study should be repeated until the values return to normal or baseline or are no longer considered clinically significant by the Investigator or Medical Monitor.

- If such values do not return to normal/baseline within a time judged reasonable by the Investigator, the etiology should be identified, and the Sponsor notified.
- If laboratory values from non-protocol-specified laboratory assessments performed at the institution's local laboratory require a change in participant management or are considered clinically significant by the Investigator (e.g., SAE or AE) they must be recorded in the eCRF.

# 8.3. Adverse Events and Serious Adverse Events

The definitions of AEs and SAEs are located in Section 10.3.

The Investigator and any qualified designees are responsible for detecting, documenting, and recording events that meet the definition of an AE or SAE and remain accountable for following up AEs that are serious, considered related to the study intervention or study procedures, or that caused the participant to discontinue the study intervention (see Section 7.1).

### 8.3.1. Time Period and Frequency for Event Assessment

All AEs/SAEs will be collected from the signing of the ICF until the last day of study participation, including F/U.

Any medical condition that is present at the time that the participant is screened will be considered as baseline medical history and not reported as an AE. However, if the study participant's condition deteriorates after having received the first dose of Investigational Product during the study, it will be recorded as a TEAE.

Investigators are not obligated to actively seek AE or SAE after the conclusion of the study participation. However, if the Investigator learns of any SAE, including death, at any time after a participant has been discharged from the study, and he/she considers the event to be reasonably related to the study intervention or study participation, the Investigator must notify the Sponsor promptly.

### 8.3.2. Method of Detecting AEs and SAEs

The method of recording, evaluating, and assessing causality of AE and SAE and the procedures for completing and transmitting SAE reports are provided in Section 10.3.

AE or SAEs will be reported by the participant or observed by the study staff. Care will be taken not to introduce bias when detecting AEs and/or SAEs. Open-ended and non-leading verbal questioning of the participant is the preferred method to inquire about AE occurrences, for example, "Have you noticed anything different since you started the study?". The occurrence of an AE or SAE may also be detected upon review by a study monitor.

# 8.3.3. Follow-up of AEs and SAEs

After the initial AE/SAE report, the Investigator is required to proactively follow each participant at subsequent visits/contacts. All SAEs and non-serious AESI; as defined in

Section 10.3.3) will be followed until resolution, stabilization, the event is otherwise explained, or the participant is lost to follow-up (as defined in Section 7.3). Further information on follow-up procedures is given in Section 10.3.

### 8.3.4. Serious Adverse Event Reporting

All SAEs will be recorded and reported to the Sponsor or designee immediately; under no circumstance should this exceed 24 hours, as indicated in Section 10.3.5. The Investigator will submit any updated SAE data to the Sponsor within 24 hours of it being available.

Prompt notification by the Investigator to the Sponsor of a SAE is essential so that legal obligations and ethical responsibilities towards the safety of participants and the safety of the study intervention under clinical investigation are met.

The Sponsor has a legal responsibility to notify both the local regulatory authority and other regulatory agencies about the safety of a study intervention under clinical investigation. The Sponsor will comply with country-specific regulatory requirements relating to safety reporting to the regulatory authority, IRB/IEC, and Investigators.

Investigator safety reports will be prepared for SUSAR according to local regulatory requirements and Sponsor or Sponsor's designee's policy and will be forwarded to Investigators as necessary.

# 8.3.5. Reporting of Pregnancy

Details of all pregnancies in female participants and female partners of male participants will be collected after the start of study intervention and until 24 weeks after the last dose.

If a pregnancy is reported, the Investigator should inform the Sponsor within 24 hours of learning of the pregnancy and should follow the procedures outlined in Section 10.4.4.

While pregnancy itself is not considered to be an AE or SAE, any pregnancy complication or elective termination of a pregnancy for medical reasons will be reported as an AE or SAE. Abnormal pregnancy outcomes (e.g., spontaneous abortion, fetal death, stillbirth, congenital anomalies, ectopic pregnancy) are considered SAEs.

The participant or pregnant partner will be followed to determine the outcome of the pregnancy. The Investigator will collect follow-up information on the participant or pregnant partner and the neonate, and the information will be forwarded to the Sponsor.

Any post-study pregnancy-related SAE considered reasonably related to the study intervention by the Investigator will be reported to the Sponsor as described in Section 8.3.4. While the Investigator is not obligated to actively seek this information in former study participants, he or she may learn of an SAE through spontaneous reporting.

# 8.3.6. Adverse Events of Special Interest

AEs of special interest (AESI; as defined in Section 10.3.3), will be followed until resolution or stabilization, the event is otherwise explained, or the participant is lost to follow-up (as defined in Section 7.3).

# 8.4. Treatment of Overdose

For this study, any dose of study intervention greater than the protocol-specified dose will be considered an overdose.

In the event of an overdose, the Investigator should:

- 1. Immediately contact the Medical Monitor.
- 2. Closely monitor the participant for any AE/SAE and laboratory abnormalities for at least 14 days.
- 3. Obtain a plasma sample for PK analysis within 14 days from the date of the last dose of study intervention if requested by the Medical Monitor (determined on a case-by-case basis).
- 4. Document the quantity of the total dose as well as the number of injections over time.

Decisions regarding dose interruptions will be made by the Investigator in consultation with the Medical Monitor based on the clinical evaluation of the participant.

# 8.5. Pharmacokinetics

Blood samples of approximately 2.0 mL will be collected for the measurement of plasma concentrations of belcesiran, as specified in the SoA (Section 1.3).

Instructions for the collection and handling of biological samples will be provided by in the laboratory manual. The actual date and time (24-hour clock time) of each sample will be recorded.

Samples collected for analyses of belcesiran concentration may also be used to evaluate safety or efficacy aspects related to concerns arising during or after the study.

Pharmacokinetic parameters to be determined include apparent clearance (CL/F) and apparent volume of distribution (Vz/F), AUC,  $C_{max}$ ,  $T_{max}$ , and  $t_{1/2}$ , as data permit to determine the PK profile of belcesiran.

Drug concentration information that would unblind the study will not be reported to investigative sites or blinded personnel.

### 8.5.1. Metabolite Identification

Plasma metabolite identification studies may be performed by nuclear magnetic resonance, mass spectrometry, liquid chromatography-mass spectrometry, gas chromatography-mass spectrometry, Fourier transform mass spectrometry, and/or equivalent methods.

# 8.6. Pharmacodynamics

Pharmacodynamic parameters, other than serum Z-AAT protein concentrations (as described in Section 8.1.1), are not evaluated in this study.
# 8.7. Genetics

Genetics are not evaluated in this study. Genotyping will be performed locally at screening if historical data are not available for determination of study eligibility for the participants.

# 8.8. Immunogenicity Assessments

Antibodies to belcesiran will be evaluated in serum samples collected from all participants, according to the SoA (Section 1.3). Additionally, serum samples should also be collected at the final visit from participants who discontinued study intervention or were withdrawn from the study. These samples will be tested by the Sponsor or Sponsor's designee.

Samples for the detection and characterization of antibodies to belcesiran will be stored until a validated assay method is available.

# 8.9. Medical Resource Utilization and Health Economics

Medical resource utilization and health economics will not be evaluated in this study.

# 9. STATISTICAL METHODS

In general, summary statistics (n, mean, standard deviation, median, minimum and maximum values for continuous variables, and number and percentage of participants in each category for categorical variables) will be provided by treatment group and cohort for all variables.

Baseline value is defined as the last non-missing assessment prior to the first dose of study drug, except for serum AAT where baseline is defined as the mean from all predose AAT measurements.

Source data for the summary tables will be presented as by-subject data listings.

All statistical tests will be 1-sided with a type I error rate of 5%, unless otherwise specified.

Complete details of the statistical analysis will be outlined in the SAP and finalized before the interim analysis database lock.

# 9.1. Randomization and Sample Size

The study will include 3 cohorts. In Cohorts 1 and 2 there will be up to 8 participants in each cohort (randomization scheme ratio of 3:1 active:placebo). The sample size for Cohort 1 and Cohort 2 is based on clinical consideration rather than statistical power calculation.

The primary endpoint for Cohort 3 of this study is the percentage change from baseline in serum and liver Z-AAT protein concentration at week 24. Assuming the percentage change from baseline is 80%, 60% and 10% in the active high dose group, active low dose group and placebo group respectively, and the standard deviation is 0.5 for all three groups, a sample size of 10 participants per treatment group will provide at least 80% power to detect a statistically significant difference between active high dose group and placebo, and between active low dose group and placebo, at an overall 1-sided significance level of 0.05.

The F1, F2, F3, and F4 fibrosis types will be used as randomization stratification factors for all 3 cohorts.

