The 210 mg q4w dosing regimen was selected to target a near-maximal PD response. From the simulations, the mean reduction in serum AAT was predicted to be approximately 82% by Week 24 (90% prediction interval [PI]: -59.1% to -98.8%). A lower dose of 50 mg q4w was included to better characterize the dose-exposure-response relationship of belcesiran and its safety profile over a range of serum AAT reduction. Following the administration of 50 mg q4w, the mean reduction in serum AAT was predicted to be approximately 65% (90% PI: -44.5% to -82.4%) by Week 24. Simulations predicted a serum AAT reduction of at least 50% by Week 24 in about 90% of the participants receiving 50 mg q4w dose, suggesting a 50% reduction in hepatic AAT production. It has been shown that adults with the SERPINAI PiMZ genotype, which leads to an approximately 50% reduction in hepatic Z-AAT production, have lower levels of serum transaminases, fewer AAT inclusions in liver, and lower liver stiffness than adults with the PiZZ genotype, although higher than adults without the PiZ variant (Schneider et al, 2020). Therefore, the 50 mg q4w dose, which is predicted to reduce hepatic Z-AAT production (and hence the downstream serum Z-AAT) by at least 50% in the majority of study participants with AATLD, may offer some clinical benefits to most of the participants receiving this dose while expanding the range of PD response for dose-exposure-response characterization.

Monthly dose frequency has been selected for Cohorts 1 and 2 to maximize potential PD response. The first 6 months dosing in Cohort 3 will also be monthly after which patients will shift to quarterly dosing. The rationale for exploring an alternative dosing regime is out of consideration for patient burden. For the high dose explored, simulations suggest that reducing dose frequency after steady state would only have a minor effect on the PD response.

In summary, the two belcesiran doses included in the clinical protocol (210 mg and 50 mg) are predicted to result in a range of PD response that would allow for adequate characterization of belcesiran dose-exposure-response in patients with AATLD.

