# 9.3.1.2. Analysis of Serum and Liver Z-AAT Concentrations

The primary endpoint for Cohort 3 of this study is the percentage change from baseline in serum and liver Z-AAT protein concentration at week 24.

The primary endpoint for Cohort 3 will be analyzed by using a linear log-normal regression model. Statistical testing for the primary endpoint of Cohort 3 will be carried out using the Hocheberg testing procedure for the following comparisons: (active high dose vs. placebo) and (active low dose vs. placebo). The linear log-normal regression model will include treatment, baseline value (log transformed) and randomization stratification factor of fibrosis types (F1, F2, F3, and F4) as covariates.

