1 INTRODUCTION

The purpose of this Statistical Analysis Plan (SAP) is to provide a description of the statistical methods to be implemented for the analysis of study data from protocol DCR-A1AT-201, “A Phase 2, Randomized, Double-blind, Placebo-controlled Study Investigating Safety, Tolerability, Pharmacokinetics and Pharmacodynamics of Two Dose Levels of Belcesiran in Patients with Alpha-1 Antitrypsin Deficiency-Associated Liver Disease”. The SAP will be finalized prior to the final database lock. Any deviations from the SAP after database lock will be documented in the final Clinical Study Report (CSR).

The SAP reflects the planned study design as per the latest version of the protocol; however, the Sponsor made the decision to stop the trial prior to the enrollment of Cohort 3 subjects and prior to the completion of the planned study procedures for Cohorts 1 and 2 participants. Cohort 3 and related activity plan will be cancelled. Therefore, the available safety, AAT and biopsy data from Cohort 1 and Cohort 2 will be analyzed for the CSR purpose and there is no analysis planned for Cohort 3.

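### Does the missing scale for the SD of 0.5 undermine the Cohort 3 power claim?

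*Protocol*

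**What the plan says.** Protocol 9.1 defines the Cohort 3 primary endpoint as percentage change from baseline in serum and liver Z-AAT at week 24. It assumes changes of 80% (high dose), 60% (low dose) and 10% (placebo), and then says "the standard deviation is 0.5 for all three groups, a sample size of 10 participants per treatment group will provide at least 80% power" for each dose against placebo, "at an overall 1-sided significance level of 0.05". SAP 2.2.4 carries the same sentence.

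The analysis is described separately in Protocol 9.3.1.2: "The primary endpoint for Cohort 3 will be analyzed by using a linear log-normal regression model", with treatment, log-transformed baseline and fibrosis stage as covariates. For multiplicity, "Statistical testing for the primary endpoint of Cohort 3 will be carried out using the Hocheberg testing procedure" over the two dose-placebo comparisons.

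The SAP introduction records that the sponsor stopped the trial before any Cohort 3 enrolment and that "there is no analysis planned for Cohort 3". SAP 3.1.5 adds that no hypothesis tests will be performed at all.

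**The concern.** The power sentence gives its means in percent and its SD as a bare 0.5, with no unit. It names no test for the calculation and does not say how the overall alpha was handled across the two comparisons. A reader who takes the sentence at face value could read 0.5 as 50 percentage points, since the endpoint is defined as a percentage change. On that reading the low-dose difference is 50 points against an SD of 50 points, and 10 per group does not reach 80%. If that had been the sponsor's calculation, the low-dose comparison would have been underpowered and the stated justification for 30 participants would be wrong for one of its two hypotheses.

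**Working it through.** **Inputs.** From Protocol 9.1: 10 per group, SD 0.5, reductions of 80%, 60% and 10%, overall one-sided alpha 0.05. From Protocol 4.1: 30 participants allocated 2:1:2:1, that is 10 high dose, 10 low dose and 5 + 5 placebo, so 10 placebo participants means pooling the two placebo arms. From Protocol 9.3.1.2: Hochberg over two comparisons. The calculation is for one endpoint and makes no allowance for dropout or for covariates.

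**Single comparison.** With a two-sample t-test on 18 df, the noncentrality is d × √(n/2) = d × √5, where d is the difference divided by 0.5.

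| Scale of 0.5 | Comparison | d | Power at 0.05 | Power at 0.025 |
|---|---|---|---|---|
| Raw | Low dose | 0.50/0.5 = 1.00 | 69.4% | 56.2% |
| Raw | High dose | 0.70/0.5 = 1.40 | 91.4% | 84.1% |
| Log | Low dose | ln(0.9/0.4)/0.5 = 0.811/0.5 = 1.62 | 96.7% | 92.9% |
| Log | High dose | ln(0.9/0.2)/0.5 = 1.504/0.5 = 3.01 | about 100% | about 100% |

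**With Hochberg.** Both hypotheses are rejected if both p-values are at most 0.05; otherwise one is rejected if its p-value is at most 0.025. Simulation of 400,000 trials with variance pooled over three groups (27 df):

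| Reading | Low dose | High dose |
|---|---|---|
| Log-scale SD 0.5 | 97.0% | over 99.9% |
| Raw-scale SD 0.5, normal percentage change | 69.4% | 88.4% |

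The plan's figure of at least 80% for both doses is therefore reproduced on the log scale. On the raw scale it is reproduced for the high dose only. Low-dose power stays at or above 80% up to a log-scale SD of about 0.70 (81.1%) or a raw-scale SD of about 0.43 (80.8%).

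**A mixed reading.** Suppose the data are log-normal, 0.5 is the SD of the remaining fraction, and the test is on the log scale. The answer then depends on choices the documents do not make. If 0.9, 0.4 and 0.2 are arithmetic means, the log-scale SDs are about 0.52, 0.97 and 1.41, and low-dose power is 84% with pooled variance or 93% with pairwise variances. If they are medians and the variance is pooled, it is 75%. This reading settles nothing either way.

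**Which scale is plausible?** With a mean remaining fraction of 0.2 and a raw SD of 0.5, a normal model puts P(Z < −0.2/0.5) = P(Z < −0.4) = 34% of the high-dose group below zero concentration. That is impossible for a protein level. The simulations in Protocol 4.3 also point away from it: at 210 mg, "the mean reduction in serum AAT was predicted to be approximately 82% by Week 24 (90% prediction interval [PI]: -59.1% to -98.8" percent. If that interval is treated as normal, the SD is (98.8 − 59.1)/3.29 = 12.1 percentage points. For 50 mg, with an interval of 44.5% to 82.4%, it is (82.4 − 44.5)/3.29 = 11.5 points. Both are about a quarter of 50 points and far below the 43-point limit. These intervals are simulated serum AAT from a healthy-volunteer model, so they say nothing about liver Z-AAT and do not confirm 0.5 on the log scale.

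**The case for a change.** The case for acting is that the log reading is inferred and nowhere stated. The power sentence is written in percentage change, and nothing ties its SD to the model in Protocol 9.3.1.2. The name of the model does not settle the scale either. For Cohorts 1 and 2, SAP 3.4.1 uses the same name, but its sample code specifies a normal distribution with a log link and change from baseline as the response, so its residual SD is on the raw scale. One sentence would remove the doubt, and anyone reusing the calculation would otherwise inherit a figure they cannot check.

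Much of this stands. The omission is real, the SAP code shows loose use of the model's name, and only the sponsor can say which scale was used. But that code is not the Cohort 3 analysis, for which the protocol specifies a log-transformed baseline. The complaint that no test is given is also largely answered, because the model, the two comparisons, the multiplicity procedure and the one-sided level are all stated; only the link to the power sentence is missing. What remains is a gap in reporting, and no calculation has been shown to be wrong.

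A separate limit is that the figures above are for a single endpoint. Serum and liver Z-AAT are both listed as primary for Cohort 3, and the documents do not say how they combine. If both had to succeed and were independent (an assumption), low-dose power on the log scale would be about 0.970² = 94%, and high-dose power on the raw scale about 0.884² = 78%.

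**Conclusion.** The scale of the SD is missing from Protocol 9.1 and SAP 2.2.4, and the low-dose claim does depend on it: about 97% on the log scale and about 69% on the raw scale. The log scale is the natural reading beside a planned log-normal regression, and on it the claim holds for both doses. The raw scale, on which the low-dose claim fails, implies impossible concentrations for about a third of the high-dose group. The documents therefore do not show the stated power to be false.

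Nor would anything be gained by amending the text. Cohort 3 was cancelled before enrolment, no analysis of it is planned, and no hypothesis tests will be run, so no sample size, result or conclusion turns on the answer. If the study report describes the planned sample size, its author can name the scale there. The verdict rests on pooled placebo arms, 10 evaluable participants per group, one endpoint at a time, and Hochberg at one-sided 0.05.
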